6.2.1.3 Adverse Events of Special Interest

An AESI (serious or non-serious) is one of scientific and medical concern for which ongoing monitoring and rapid communication by the investigator to the sponsor can be appropriate. Adverse events of special interest for this study include liver tests that meet the criteria for potential drug-induced liver injury (DILI), in accordance with the US Food and Drug Administration (FDA) “Guidance for Industry-Drug-Induced Liver Injury: Premarketing Clinical Evaluation”.

Liver Tests and Stopping Criteria

The following 3 laboratory value criteria must be met for potential DILI, or “Hy’s Law”:

- An elevated alanine transaminase or aspartate transaminase laboratory value that is $\geq 3 \times \text{ULN}$
- An elevated total bilirubin laboratory value that is $\geq 2 \times \text{ULN}$

Fulcrum Therapeutics

Losmapimod

Protocol FIS-002-2019, Version 4.0 (COVID-19 Pandemic Emergency Amendment)

10 April 2020

- An alkaline phosphatase laboratory value that is $<2 \times \text{ULN}$

Study drug should be discontinued for subjects who meet the laboratory criteria for potential DILI as a result of within-protocol specific testing or unscheduled testing. This AESI must be reported to the sponsor within 24 hours of awareness. Further safety steps should be taken to closely observe and follow-up the event until resolution. These steps include, but are not limited to:

- Making every reasonable attempt to have the subject return to the clinic within 24 hours for repeat liver tests
- Obtaining a more detailed history of symptoms and prior or concurrent disease, concomitant medication use, alcohol use, recreational drug use, and special diets
- Repeating liver enzyme and serum bilirubin tests twice weekly. Frequency of retesting can decrease to once a week or less if abnormalities stabilize and the subject is asymptomatic
- Obtaining viral hepatitis serology
- Considering liver imaging and/or hepatology consultation

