9.2.2. Serum Chemistry

The following laboratory tests will be included: glucose, sodium, potassium, calcium, inorganic phosphate, total protein, albumin, blood urea nitrogen, creatinine, total bilirubin, alkaline phosphatase, aspartate aminotransferase, gamma-glutamyl transferase, and creatinine phosphokinase.

Summary tables presenting observed values and changes from baseline will be presented for serum chemistry tests with numeric values by treatment group for subjects in the Safety Analysis Set. Changes from baseline to each scheduled post-baseline visit will be presented. All chemistry data by subject will also be presented in a listing.

The clinical assessment of ‘Low’, ‘Normal’, or ‘High’ relative to the reference range will be summarized in shift tables comparing the baseline results to maximum value post-baseline for those subjects with results at both visits.

Results indicating liver-related abnormalities (i.e., ALT, AST, Total Bilirubin, and/or Alkaline Phosphatase) will also be summarized separately. A newly notable laboratory abnormality is defined as an abnormality observed post baseline that meets the notable criteria in [Table 9-1](#) and that did not exist at baseline. Subjects can still meet the criteria for a newly notable laboratory abnormality if the baseline value is missing. The table below displays the general variables and thresholds of interest. Subjects are considered to have notable laboratory abnormalities if his/her response falls within the specified definitions at least once during the treatment period.

Table 9-1: Notable Criteria for Laboratory Data Abnormalities – Liver Function Tests

Laboratory Variable	SI Units
AST	$\geq 3 \times \text{ULN}$
ALT	$\geq 3 \times \text{ULN}$
Total Bilirubin	$\geq 2 \times \text{ULN}$
Alkaline Phosphatase (ALP)	$\leq 2 \times \text{ULN}$
ALT or AST $> 3 \times \text{ULN}$ and total bilirubin $> 2 \times \text{ULN}$ and ALP $< 2 \times \text{ULN}$ (potential DILI or Hy's law case)	

All chemistry data by subject will be presented in a listing.

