Listing	16.2.8.1	Laboratory Results – Hematology	Safety Analysis Set	U	9.2.1	Safety		
Listing	16.2.8.2.1	Laboratory Results – Chemistry	Safety Analysis Set	R	9.2.2	Safety		
Listing	16.2.8.2.2	Laboratory Results of Subjects with Incidence of ALT/AST $\geq 3 \times$ ULN and Total Bilirubin $\geq 2 \times$ ULN and ALP $< 2 \times$ ULN	Safety Analysis Set	R	9.2.2	Safety		
Listing	16.2.8.3	Laboratory Results – Urinalysis	Safety Analysis Set	R	9.2.3	Safety		
Listing	16.2.8.4	Laboratory Results – Coagulation	Safety Analysis Set	R	9.2.4	Safety		
Listing	16.2.8.5	Vital Sign Results	Safety Analysis Set	U	9.3	Safety		
Listing	16.2.8.6	Electrocardiogram Results	Safety Analysis Set	U	9.5	Safety		

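### SAP Table 9-1 treats alkaline phosphatase at or below 2 × ULN as a notable abnormality in its own right, so the ALP line of the notable-liver table cannot show elevated ALP

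*SAP*

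**What the plan says.** SAP 9.2.2 announces a separate liver summary: "Results indicating liver-related abnormalities (i.e., ALT, AST, Total Bilirubin, and/or Alkaline Phosphatase) will also be summarized separately". Table 9-1 supplies the criteria. Its stand-alone rows are AST ≥3, ALT ≥3, total bilirubin ≥2 and ALP ≤2 × ULN. A last row gives the combination for potential DILI or Hy's law: ALT or AST >3, total bilirubin >2 and ALP <2 × ULN.

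Two rules turn these rows into flags. The first is "Subjects are considered to have notable laboratory abnormalities if his/her response falls within the specified definitions at least once during the treatment period". The second covers new findings: "A newly notable laboratory abnormality is defined as an abnormality observed post baseline that meets the notable criteria in" Table 9-1, provided it was absent at baseline. The SAP adds: "Subjects can still meet the criteria for a newly notable laboratory abnormality if the baseline value is missing".

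The criteria feed Table 14.3.4.2.3 (Safety Analysis Set) and its repeat, 14.3.4.2.3.1, for the pre-COVID open-label set.

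Protocol 6.2.1.3 uses low ALP only jointly: "The following 3 laboratory value criteria must be met for potential DILI". There the transaminase condition is ≥3 × ULN. The bilirubin condition is "An elevated total bilirubin laboratory value that is" ≥2 × ULN. The ALP condition is <2 × ULN. Listing 16.2.8.2.2 (SAP 15.9), whose title begins "Laboratory Results of Subjects with Incidence of ALT/AST", uses the same signs as the protocol.

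**The concern.** In the Hy's law combination, a low ALP is a qualifying condition that helps to interpret raised transaminase and bilirubin. On its own it is not an abnormality. As a stand-alone row in a table of liver abnormalities, ALP ≤2 × ULN points the opposite way from the three rows above it. The summary would count ordinary values and pass over marked elevations.

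Liver safety is a stated interest of this trial. Protocol 1.5 reports hepatotoxicity after repeat dosing with some p38 MAPK inhibitors and says that its applicability to losmapimod is unknown. A notable-liver table whose ALP line cannot register an elevation gives false reassurance, or an implausible count that has to be explained.

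A smaller inconsistency sits in the same table. SAP 9.1 sends the reader to 9.2.2 for the liver criteria that define the adverse event of special interest (AESI), and AESI incidence is a secondary endpoint (Protocol 7.1.2, SAP 3.2.2). The combined row's strict inequalities do not match the protocol or the listing.

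**Working it through.** The plan states no figure to reproduce here. The check applies the written rules to example values.

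**Inputs.** ALP criterion ≤2 × ULN, the at-least-once rule and the newly-notable rule, all from SAP 9.2.2. Enrolled subjects: 80 (Protocol 3.1.1, SAP 3.1). Subjects who had rolled over to open-label losmapimod: 12 (same sections).

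**1. Single values, at-least-once rule.** For comparison, the last column keeps the cut-off and reverses the direction to match the other stand-alone rows.

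| ALP (× ULN) | As written (≤2) | Direction reversed (≥2) |
|---|---|---|
| 0.5, 1.0, 1.5, 1.99 | flagged | not flagged |
| 2.0 | flagged | flagged |
| 2.01, 3, 5 | not flagged | flagged |

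**2. Trajectories, newly-notable rule.** A subject is flagged if the post-baseline value meets the criterion and the baseline value either did not or is missing.

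| Baseline → post-baseline (× ULN) | As written | Direction reversed |
|---|---|---|
| 0.7 → 0.7 | no | no |
| 0.7 → 3 | no | yes |
| 1.5 → 3 | no | yes |
| 3 → 0.7 | yes | no |
| 3 → 1.5 | yes | no |
| missing → 0.7 | yes | no |
| missing → 3 | no | yes |

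As written, the rule picks up recoveries, and normal values with no baseline. It misses every rise above 2 × ULN.

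**3. Count under the at-least-once rule.** The documents do not say what share of subjects will have at least one post-baseline ALP at or below 2 × ULN. Assume 95–100%:

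- 0.95 × 80 = 76
- 1.00 × 80 = 80

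This count does not carry over to the newly-notable rule, under which a subject normal throughout is not flagged (first row of step 2).

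**4. Combined row against the other definitions.**

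| Source | ALT or AST | Total bilirubin | ALP |
|---|---|---|---|
| SAP Table 9-1, combined row | >3 | >2 | <2 |
| Protocol 6.2.1.3 | ≥3 | ≥2 | <2 |
| SAP Listing 16.2.8.2.2 | ≥3 | ≥2 | <2 |

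Take a subject with ALT exactly 3.0, bilirubin 2.5 and ALP 1.0 × ULN. This subject meets the protocol and listing definitions but not the combined row. With ALT at 3.1 all three agree, so the sources differ only when a value sits exactly on a limit.

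**5. Later correction.** The SAP addendum says it also corrects typographical errors. Its sections do not mention Table 9-1, so the row stands.

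**The case against.** The strongest reply is that little depends on this row, and most of that reply stands.

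- *A reader might infer that ALP elevations disappear from the safety reporting.* They do not. SAP 9.2.2 includes ALP in the by-visit change-from-baseline tables (14.3.4.2.1), in the low/normal/high shift tables from baseline to the maximum post-baseline value (14.3.4.2.2), and in the full listing (16.2.8.2.1). A between-arm difference in shifts to high ALP would be visible there.
- *A reader might infer that the AESI or Hy's law count is distorted by the reversed row.* It is not. Those counts rest on the three-part joint definition, where low ALP is intended. The stand-alone row feeds none of them.
- *A reader might take 76–80 of 80 as established.* It is conditional on the assumed 95–100% and on the table applying the at-least-once rule. The table shells are in a separate document (SAP 4.1), so the SAP text does not settle which rule is programmed. Table 14.3.4.2.3.1 concerns only the 12 rollover subjects, so the figure does not apply to it.
- *A reader might say that no elevation is ever flagged.* That is exact only above 2 × ULN. Values between 1 and 2 × ULN are flagged, but cannot be told apart from normal ones.
- The ≤ sign was read by machine from a PDF, and every other ALP condition in the documents reads <. The source should be checked. A strict < would still point the wrong way; only ≥ or > would remove the problem. That the row was copied from the Hy's law combination is a likely explanation, not something the documents state.

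The table is also descriptive and is not marked for topline or interim delivery, and an output flagging nearly everyone would probably be noticed. These points limit the consequence. None supplies a reading under which a normal ALP is a notable liver abnormality.

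**Conclusion.** The stand-alone ALP criterion in Table 9-1 is wrong as written under both flagging rules, and the addendum does not correct it. The consequence is confined to the ALP line of Tables 14.3.4.2.3 and 14.3.4.2.3.1, which cannot show ALP elevation. No efficacy result, hypothesis test, AESI count or potential-DILI count depends on that line.

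The mismatch between > and ≥ in the combined row is a separate, smaller matter. It can change an AESI count taken from Table 9-1, but only for a subject with a value exactly at 3.0 or 2.0 × ULN.

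Overall this is a minor but real correction to a descriptive safety table. The conclusion rests on the ≤ sign being confirmed in the source PDF.

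**What to change.** 1. Confirm the ALP sign in the source PDF.
2. In Table 9-1, either delete the stand-alone ALP row or restate it as an elevation. The documents give no stand-alone high-ALP cut-off, so the sponsor must set one; the same 2 × ULN limit with the direction reversed is one example. Keep ALP <2 × ULN only inside the combined row.
3. Reconcile the inequality signs of the combined row with Protocol 6.2.1.3 and Listing 16.2.8.2.2, so that one definition is counted throughout. Protocol 6.2.1.3 also attaches a study-drug discontinuation rule to these criteria, so this review does not say which signs are right.
4. State in the SAP whether Table 14.3.4.2.3 counts notable or newly notable findings.

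The cost is a few table cells, one sentence and the matching program lines, and it needs no new data.

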9.2.3. Urinalysis

The following laboratory tests will be included: leukocytes, blood, nitrite, protein, urobilinogen, bilirubin, pH, specific gravity, ketones, and glucose.

Summary tables presenting observed values and changes from baseline will be presented for urinalysis tests with numeric values by treatment group for subjects in the Safety Analysis Set. Changes from baseline to each scheduled post-baseline visit will be presented.

All urinalysis data by subject will be presented in a listing.

9.2.4. Other Laboratory Tests

The following coagulation tests will also be reported: International normalized ratio, prothrombin time, and partial thromboplastin time. These parameters will be presented and summarized in the same manner to that described in [Section 9.2.1](#).

9.3. Vital Sign Measurements

Summary tables will be presented for vital sign data, including pulse rate, respiration rate, blood pressure, and temperature by treatment for subjects in the Safety Analysis Set. Observed results at each visit will be presented. Change from baseline to each post-dose assessment will also be presented. All vital sign data by subject will also be presented in a listing.

9.4. Physical Examination

A table will summarize physical examination results by treatment for the Safety Analysis Set. Status of a body system and any finding associated with the body system as normal, abnormal, or

not done will be captured at screening and safety follow-up. Physical examination results for all subjects will also be presented in a listing.

A separate table will be presented for the summary of neurological examination results. The scores collected in the CRF which is in ordinal scales will be converted into numeric scales according to the convention provided below.

MMT score as collected in the CRF	Numeric Scale
0	0
1	1
2	2
3-	2.67
3	3
4-	3.67
4	4
4+	4.33
5-	4.67
5	5

A total and average of the numeric score will be derived for upper extremity, lower extremity, and all muscle groups.

The following are the components of the upper extremity:

- Deltoid MRC Score Right
- Deltoid MRC Score Left
- Shoulder Abduction MRC Score Right
- Shoulder Abduction MRC Score Left
- Triceps MRC Score Right
- Triceps MRC Score Left
- Biceps MRC Score Right
- Biceps MRC Score Left
- Wrist Extension MRC Score Right
- Wrist Extension MRC Score Left
- Wrist Flexion MRC Score Right
- Wrist Flexion MRC Score Left
- Finger Extension MRC Score Right
- Finger Extension MRC Score Left
- Finger Flexion MRC Score Right
- Finger Flexion MRC Score Left
- Grip MRC Score Right
- Grip MRC Score Left

The following are the components of the lower extremity:

- Hip Flexion MRC Score Right

- Hip Flexion MRC Score Left
- Knee Extension MRC Score Right
- Knee Extension MRC Score Left
- Knee Flexion MRC Score Right
- Knee Flexion MRC Score Left
- Hip Abduction MRC Score Right
- Hip Abduction MRC Score Left
- Hip Adduction MRC Score Right
- Hip Adduction MRC Score Left
- Ankle Dorsiflexion MRC Score Right
- Ankle Dorsiflexion MRC Score Left
- Plantarflexion MRC Score Right
- Plantarflexion MRC Score Left

Total score in the upper extremity is derived as the sum of numeric scores of muscles included in the upper extremity. Total score in the lower extremity is derived as the sum of numeric scores of muscles included in the lower extremity. Total score in all muscle groups is the sum of numeric scores of muscles in the upper and lower extremities plus the numeric score in neck flexion and neck extension.

Average score in the upper extremity is the sum of numeric scores of muscles included in the upper extremity divided by 18. Average score in the lower extremity is the sum of numeric scores of muscles included in the lower extremity divided by 14. Average score in all muscle groups is the sum of numeric scores of muscles in the upper and lower extremities and numeric scores in neck flexion and neck extension divided by 34.

Neurological examination results for all subjects will also be presented in a listing.

9.5. Electrocardiogram

All subjects will have a standard 12-lead ECG performed during the study as clinically indicated. Electrocardiogram data for all subjects will also be presented in a listing.

Descriptive summaries will be provided for the ECG data including ventricular rate (bpm), PR interval (msec), QRS duration (msec), QT interval (msec), and QTcF interval (msec) by treatment group for subjects in the Safety Analysis Set. In addition, number and percentage of subjects with normal sinus rhythm will also be presented in a table. Observed results at each visit will be presented. Change from baseline to each post-dose assessment will also be presented.

The number and percentage of subjects with an overall evaluation of ‘Normal’, ‘Abnormal, Not Clinically Significant’, or ‘Abnormal, Clinically Significant’ will be presented for baseline, Week 4, Week 48, End of Treatment, and Safety Follow-up.

A categorical summary of QTcF values and change from baseline at each visit will be presented by number and percentage for the Safety Analysis Set. Categories for reporting absolute QTcF interval are defined as: >450 to 480 msec, >480 to 500 msec, and >500 msec. Change from baseline in QTc interval is classified as: >30 to 60 msec increase from baseline and >60 msec increase from baseline.

ECG data for all subjects will also be presented in a listing.

10. Pharmacokinetics

By-subject listing of pharmacokinetic blood sample and muscle sample collection times as well as derived sampling time deviations will be provided. Losmapimod plasma and muscle concentrations will be summarized using descriptive statistics (n, mean, standard deviation, minimum, median, maximum, coefficient of variation) by scheduled time point. Concentrations that are below the limit of quantitation (BLQ) will have a value of LLOQ value divided by 2 in the computation of descriptive statistics. Mean concentration-time data will be graphically presented. All data presentation will use the PK Analysis Set.

Predose samples that are missing will be assigned as missing.

Concentrations assigned a value of missing will be omitted from the calculation of descriptive statistics. A concentration value of zero will be included for the computation of arithmetic mean. If 50% or more of the values are BLQ at one scheduled time point, the arithmetic mean will be reported as BLQ.

The individual and mean plasma concentrations and the individual and mean concentrations in skeletal muscle biopsies will be presented by scheduled time point in figures on linear scales.

11. Pharmacodynamics

For each treatment, descriptive statistics of natural log (ln) transformed pHSP27 concentrations in blood will be presented at Baseline, Week 16, and Week 36 as well as change from baseline at Week 16 and Week 36. An MMRM model will be used to analyze the change from baseline in ln-transformed pHSP27 in blood with repeat number category, treatment group, visit, and treatment-by-visit interactions as fixed effects and baseline value of ln-transformed pHSP27 in blood as a covariate. Within-group LS mean changes from baseline, the associated SEs and 2-sided 95% CIs, treatment differences in LS mean changes from baseline at post-baseline visits and the associated 2-sided 95% CIs and 2-sided p-values will be derived from the MMRM model and will be provided in the summary table. An unstructured covariance matrix will be used to model the correlation among repeated measurements within each subject. If models using unstructured covariance do not converge, an AR(1) covariance structured will be used instead. Similar methods will be used to analyze the change from baseline in ln-transformed values of total pHSP27 and ln-transformed values of pHSP27 to total HSP27 ratio in blood. Similar methods will be used to analyze the change from baseline within subgroups identified in [Section 4.6 \(#1 - #3\)](#) to evaluate

consistency of treatment effects across the subgroups. For the repeat category subgroup analysis, the repeat category will be excluded as fixed effect from the model.

Point estimates (i.e., LS means) will be back transformed using the exponential function to tabularly and graphically present the ratio of postbaseline to baseline in pHSP27. Percent change from baseline, calculated as the difference in the ratio of postbaseline to baseline minus 1 times 100, will also be tabularly and graphically presented.

Population PK and PK/PD models may be developed to address program objectives that require an integrative interpretation of these study results. These may include investigations of the nature of the PK/PD relationship and the use of these study results as part of a larger model-based data analysis. If population PK and PK/PD analyses are performed, those results will be reported separately from the results of this study.

12. Interim Analysis

Initially, no interim analysis for efficacy was planned. However, based on protocol version 4.0 (COVID-19 Pandemic Emergency Amendment) dated 10Apr2020, an interim analysis was included to provide timely data to inform the further development of losmapimod for the treatment of FSHD.

One IA will be performed when a minimum of 22 paired muscle biopsies are completed. A group sequential method (O'Brien-Fleming Spending Function) will be used to ensure an overall significance level of 0.05 (double-sided) due to multiple looks at the DUX4 primary endpoint, if the IA is deemed necessary by the Sponsor.

- With a sample size of approximately 22 subjects at IA, the test alpha at IA is approximately 0.001, and the final test alpha is 0.05. If the p-value from the test is <0.001 , then the study may be stopped for efficacy, or continue as planned as decided by the Sponsor. Cumulative exit probability under the alternative hypothesis is approximately 2.3% and approximately 82.3% at the IA and final analysis, respectively (SAS Version 9.4; nQuery 8 – Power and Sample Size for Group Sequential Trials, Version 8.5.1.0).
- With a sample size of 32 subjects at IA, the test alpha at IA is approximately 0.004, and the final test alpha is 0.048. If the p-value from the test is <0.004 , then the trial may be stopped for efficacy, or continue as planned as decided by Sponsor. Cumulative exit probability under the alternative hypothesis is approximately 13.9% and approximately 82.2% at the IA and final analysis, respectively (SAS Version 9.4; nQuery 8 – Power and Sample Size for Group Sequential Trials, Version 8.5.1.0).

The alpha at the time of the IA for sample size ranging from 22 to 32 are provided in [Table 12-1](#)

Table 12-1 Alpha at Interim Analysis and Final Analysis for Different Sample Sizes at Interim Analysis (O'Brien Fleming Method)

Interim Analysis Sample Size	Alpha at Interim Analysis	Alpha at Final
22	0.000567	0.049755
23	0.000736	0.049685
24	0.000951	0.049596
25	0.001203	0.049493
26	0.001474	0.049384
27	0.001803	0.049253
28	0.002173	0.049107
29	0.002556	0.048959
30	0.003005	0.048787
31	0.003496	0.048602
32	0.004027	0.048405

The DUX4, PK, demographics, disposition data and sub-group analysis on the DUX4 endpoint ([Section 4.6, #1 to #5](#) and [#11](#)) will be presented to the Sponsor as group-level summaries of the unblinded data with associated p-values. The respective tables are indicated in the List of Planned Summary Tables.

13. Safety Review Committee (SRC)

A SRC will be appointed for the study. The primary responsibility of the SRC will be to act in an advisory capacity to the Sponsor to safeguard the interests of trial patients by monitoring patient safety, assess patient risk versus benefit, and assess data quality and general evaluation of the trial progress. Its activities will be delineated in a SRC charter that will define the membership, responsibilities and the scope and frequency of data reviews. The SRC may have an organizational meeting prior to commencement of the trial. The SRC will have meetings where it will review blinded data during a closed session. These meetings will be planned at regular intervals. They may convene ad hoc meetings based on rates of SAEs if safety concerns arise during the trial. After its assessment, the SRC will recommend continuation, modification or termination of the clinical trial.

The blinded team will prepare the safety tables, listings and/or figures using the dummy randomization and materials/kits schedule.

14. References

Lemmers RJ, van der Vliet PJ, Klooster R, et al. A unifying genetic model for Facioscapulohumeral Muscular Dystrophy. *Science*. 2010;329(5999):1650-3.

Statland JM and Tawil R. Risk of functional impairment in facioscapulohumeral muscular dystrophy. *Muscle Nerve*. 2014;49(4):520-7.

